Patients with intractable neuropathic lower extremity pain related to DPN that fulfill inclusion and exclusion criteria (see below) will be considered for participation in this prospective feasibility study. Baseline testing will be performed to exclude confounding factors that may affect outcomes (figure). All patients that are candidates for SCS undergo a spinal cord stimulation trial as part of standard clinical care with all of the FDA approved indications. If the patient is deemed a candidate and complying with this standard clinical practice, the patient will undergo a HF10 SCS (Nevro Senza®) trial lasting up to 14 days with an external stimulator to determine short term response.⁵⁶ Patients with 40% or greater pain reduction from baseline will be eligible to proceed to permanent implantation.⁵⁶ Patients with HF10 SCS will receive 30 μ s pulses delivered at 10,000 Hz with amplitude adjusted to optimal analgesic response. Programming will occur postoperatively and as needed based on patient feedback in standard clinic visits.⁵⁶ At 6 month follow-up, paresthesia mapping will be performed during the programming visit in which the subthreshold SCS will be temporary increased during a 10 minute protocol to a perceived level to determine the dermatomal stimulation pattern with the SCS lead placement.

Implant Procedures

The SCS implant will follow standard clinical practice for these FDA approved indications. Two percutaneous leads will be placed in the posterior spinal epidural space under radiographic guidance and attached to either an external stimulator (trial phase) or a subcutaneously implanted impulse generator (IPG). The distal tip of one lead will be placed at the top of the T8 vertebral body and the second lead tip will be placed at the mid T9 vertebral level for maximal electrode coverage at the T9/T10 junction.⁵⁶ A subcutaneous pocket will be created using standard surgical techniques for placement of an IPG. The leads, anchored to the supraspinous fascia, will be tunneled to the pocket site and connected to the IPG. Intraoperative impedance testing will be performed to ensure electrical integrity.⁵⁶

Outcome Assessments

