Adverse events will be monitored throughout the study (e.g. infection, lead migration). Lead migration will be defined as loss of efficacy that could not be remedied by reprogramming and confirmed radiologically.⁵⁶ Baseline testing will be performed either prior to SCS trial or a minimum of two weeks following removal of SCS trial leads and prior to SCS implant. During outcome assessments, the spinal cord stimulator will remain active and any medications that can impact autonomic testing will be discontinued prior to each test.

Assessments of pain will be made with the numeric rating scale (NRS) for each of the time points. The patient will be contacted at 5 and 11 months to set up in-person assessment appointments. At this time, the NRS will be used. If the NRS is ≥ 3 the principal investigator will be notified and the patient will have an appointment for a SCS assessment prior to the 6 and 12 month assessment. Neuropathic symptoms will be monitored with the Neuropathy Symptoms and Change (NSC) scale at 6 months and 12 months to assess impact on neuropathic pain (figure).⁶² Patient Health Questionnaire (PHQ9) will be assessed at baseline, 6 months and 12 months to monitor for the presence and severity of depression. A body mass index (BMI) and Hemoglobin A1C (HgA1C) will be done at baseline and at 12 months. The presence of allodynia and/or hyperalgesia will be monitored throughout the course of the study with the modified Leeds Assessment of Neuropathic Symptoms and Signs (S-LANSS).⁶³ Small fiber sudomotor function with Q-SWEAT will be assessed periodically during the study (baseline, 6 months, and 12 months) (figure).^{28, 53, 58, 59, 64, 65}

Gross neurologic function will be assessed by a board certified neurologist at baseline, 6 months, and 12 months, and the neuropathy impairment score (NIS) of the lower limbs with lower limb function test (LLF) will be calculated for an objective comparative assessment.^{66, 67} EMG will be performed at baseline (partly to exclude mimickers of DPN) and at 12 months to compare nerve conduction studies (NCS) for an objective assessment of large fiber nerve function(figure).⁶⁷ Only the NCS of the lower limb will be performed with the EMG at 12 months (no needle EMG will be performed at 12 months). The Oswestry Disability Index (ODI) will be used as a gross functional assessment at each of the time points.

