Resources: *Describe the available resources to conduct the research (personnel, time, facilities, mentor commitment, etc.):*

1. Clinical research coordinator to aid in implementation of the study
2. Periodic testing (Q-SWEAT and Laser Doppler flowmetry) will be performed in the Clinical Research Unit (CRU)

(1a) This is a multisite study involving Mayo Clinic and non Mayo Clinic sites. *When checked, describe in detail the research procedures or activities that will be conducted by Mayo Clinic study staff.*

(1b) Mayo Clinic study staff will be engaged in research activity at a non Mayo Clinic site. *When checked, provide a detailed description of the activity that will be conducted by Mayo Clinic study staff.*

Subject Information

Target accrual is the proposed total number of subjects to be included in this study at Mayo Clinic. A "Subject" may include medical records, images, or specimens generated at Mayo Clinic and/or received from external sources.

Target accrual: 20 patients over the course of a 2 year enrollment period (3 years in total for completion of study).

Subject population (children, adults, groups): Patients with the FDA approved indication of medically intractable painful DPN age 18 and over that are appropriate surgical candidates and without severe autonomic neuropathy or psychiatric comorbidity that would preclude SCS implant.

Inclusion Criteria:

- ≥ 18 years of age
- Type 2 diabetes mellitus
- Refractory predominantly lower extremity neuropathic pain for > 1 year
- Presence of length dependent peripheral neuropathy on sudomotor testing (Q-SWEAT)
- Completed spinal cord stimulation trial with 40% or greater pain reduction from baseline
- Failed medication trials or contraindication to gabapentinoid medications (gabapentin, pregabalin) and/or serotonin/norepinephrine reuptake inhibitors (tricyclic antidepressant (TCA) or duloxetine or venlafaxine)
- Average pain score on a numeric rating scale of ≥ 5 (with 0 representing no pain and 10 the worst pain imaginable)
- Appropriate surgical candidate for SCS⁵⁶

Exclusion Criteria:

- Severe Autonomic Neuropathy as measured by the composite autonomic scoring scale (10 point scale) with a score ≥ 7 ^{52, 64}
- History of sympathectomy⁵²
- Uncontrolled arterial hypertension (Systolic Blood Pressure >160)^{26, 27}
- Baseline Foot TcPO₂ < 10 mmHg to exclude patients with severe peripheral arterial disease^{28, 29}
- Hemoglobin A1c $> 8\%$ ^{68, 69}

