Account, member, certificate or professional license numbers, health beneficiary numbers		
Vehicle identifiers and serial numbers, including license plate numbers		
Check 'None' when none of the identifiers listed above will be recorded, maintained, or shared during the conduct of this study. (exempt category 4)	 None	 None

Data Analysis

Power analyses and study endpoints are not required for minimal risk research, pilot or feasibility studies.

No statistical information. *If checked, please explain:* feasibility study.

Power Statement:

This is a feasibility study and so a power analysis was not performed.

Data Analysis Plan: Demographic data will be reported with descriptive statistics, including means with SD's for continuous data and percentages and counts for categorical data. Assuming a normal distribution, two-sided paired *t* tests and analysis of covariance (ANCOVA) will be used to compare means in VAS/NRS pain scores, NSC, ODI, NIS, LLF, and S-LANSS scores at the corresponding time points as the primary endpoints(figure). In addition, two-sided paired *t* tests and analysis of covariance (ANCOVA) will be used to compare means for amplitudes (mA) and conduction velocity (m/s) on NCS with EMG at baseline and 12 months post-implant. The secondary endpoints will be assessed with two-sided paired *t* tests and analysis of covariance (ANCOVA) for latency (min) and sweat output ($\mu\text{L}/\text{cm}^2$) on Q-SWEAT and arbitrary perfusion units on Laser Doppler flowmetry (p.u.) at baseline, 6 months, and 12 months post-implant.

Endpoints:

[figure not shown]
Primary: Changes in VAS/NRS, NSC, ODI, NIS, LLF, and S-LANSS.

Secondary: Changes in latency (min) and sweat output ($\mu\text{L}/\text{cm}^2$) on Q-SWEAT, arbitrary perfusion units (p.u.) on Laser Doppler flowmetry, and amplitudes (mA) and conduction velocity (m/s) on NCS when compared to baseline. Changes in BMI, HgA1C and PHQ9 scores when compared to baseline.

FIGURE

Quantitative Assessment of Painful Diabetic Peripheral Neuropathy after High Frequency Spinal Cord Stimulation: (QUANT) HF10 Study

REFERENCES:

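### Paired t tests and ANCOVA are planned for the same before-after comparisons in a one-group study of 20, with no ANCOVA model and no lead result, and the 12-month paired test sets aside patients who miss month 12

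*Combined protocol and SAP*

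**What the plan says.** The Methods section describes one cohort whose members "will be considered for participation in this prospective feasibility study". No control group or randomisation appears anywhere. Under Subject Information the size is given as "Target accrual: 20 patients over the course of a 2 year enrollment period".

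The Data Analysis Plan joins paired t tests and ANCOVA three times:
- For the six primary scores: "analysis of covariance (ANCOVA) will be used to compare means in VAS/NRS pain scores, NSC, ODI, NIS, LLF, and S-LANSS scores".
- For nerve conduction studies (NCS), at baseline and 12 months.
- For Q-SWEAT and Laser Doppler, at baseline, 6 and 12 months. This sentence opens "The secondary endpoints will be assessed with two-sided paired" and again adds ANCOVA.

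None of the three gives a factor, a covariate, a within-patient term or an order of precedence. The plan states no alpha, no lead time point and no rule for missed visits. The Endpoints section also lists "Changes in BMI, HgA1C and PHQ9 scores when compared to baseline" as secondary, but the analysis plan assigns these no test.

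The nearest hint of covariate adjustment is in Methods: "Baseline testing will be performed to exclude confounding factors that may affect outcomes". That sentence concerns baseline testing and names no covariate. Outcome Assessments adds two phone-stage pain readings: "The patient will be contacted at 5 and 11 months to set up in-person assessment appointments. At this time, the NRS will be used".

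**The concern.** With no between-patient groups, ANCOVA has no default meaning here, so the analyst must invent the model. Some forms are sound, for example visit as a factor with patient as a block. Others are not. Regressing change on baseline centred at the sample mean, and testing the intercept, returns the same mean change as the paired t test but with a smaller standard error, because it treats the sample's baseline mean as if it were known. Two p-values per endpoint, with neither named as the lead, leave room for different conclusions from the same 20 patients.

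The second issue is missed visits. The 12-month paired test uses only patients with a 12-month reading. A patient seen at month 6 but not at month 12 drops out of it, although the 6-month value is informative about month 12. If patients doing worse at month 6 are more likely to be lost, the 12-month benefit is overstated even though data that would correct it were collected.

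**Working it through.** The plan has no power figure or derived sample size to reproduce. From the documents: n = 20, two-sided tests, visits at baseline, 6 and 12 months, pain entry cut "Average pain score on a numeric rating scale of ≥ 5". Everything else is assumed: alpha 0.05, normal data, and the SDs, correlations and losses below.

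**1. Standard error of the centred ANCOVA relative to the paired t test.** With SDs s1 (baseline) and s2 (follow-up) and correlation r, the ratio is

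sqrt[ s2²(1 − r²) / (s1² + s2² − 2·r·s1·s2) ],

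which reduces to sqrt[(1 + r)/2] when s1 = s2.

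- Equal SDs: r = 0.3 gives sqrt(0.65) = 0.806; r = 0.5 gives sqrt(0.75) = 0.866; r = 0.7 gives sqrt(0.85) = 0.922.
- SDs 1.4 and 2.2, r = 0.4: numerator 4.84 × 0.84 = 4.066; denominator 1.96 + 4.84 − 2.464 = 4.336; ratio sqrt(0.938) = 0.968.

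The unequal case is plausible for pain, because the entry cut narrows the baseline spread. The other scores and NCS have no such cut.

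**2. Rejection rates, by simulation at n = 20.**

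| Setting | Paired t, no change | Centred ANCOVA, no change |
|---|---|---|
| Equal SDs, r = 0.3 | 5.0% | 10.8% |
| Equal SDs, r = 0.5 | 5.0% | about 8.5% |
| Equal SDs, r = 0.7 | 5.0% | about 6.8% |
| SDs 1.4 and 2.2, r = 0.4 | 5.0% | 5.7% |

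With a true fall of 1 point, the two methods disagree on significance in 6.6% of samples (SDs 1.5, r = 0.5) or 3.7% (SDs 1.4 and 2.2, r = 0.4).

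**3. Patients missing month 12.** Assumed pain means are 7.0 at baseline and 4.2 at months 6 and 12 (true change −2.80). SDs are 1.4, 2.2 and 2.2. Correlations are 0.4 with baseline and 0.75 between months 6 and 12. With all 20 patients the standard error of the change is sqrt(4.336)/sqrt(20) = 2.082/4.472 = 0.47, hence a sampling SD of about 0.5.

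Soft selection means 1 log-odds of loss per SD of the score. Strong selection means losing the highest values of score plus noise of SD 1. Entries are the overstatement of benefit, in points, with 2 and 4 of 20 lost:

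| Loss depends on | Paired t test | Model using all three visits |
|---|---|---|
| 6-month pain, soft | 0.10, 0.20 | at most 0.01 |
| 6-month pain, strong | 0.18, 0.33 | at most 0.01 |
| Unseen 12-month pain, soft | 0.15, 0.30 | 0.09, 0.19 |
| Unseen 12-month pain, strong | 0.27, 0.50 | 0.18, 0.35 |

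With 4 lost by 6-month pain, root mean squared error is 0.56 for the paired test against about 0.51 for the model (soft), and 0.61 against 0.52 (strong). In the last two rows the model removes only about 30-40% of the bias: for example (0.50 − 0.35)/0.50 = 30% and (0.15 − 0.09)/0.15 = 40%.

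**4. Complete data.** A REML mixed model with visit as fixed effect and unstructured covariance gives the paired-t result. One simulated data set fitted both ways gave a change of −2.4097 and a standard error of 0.4466 in each.

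**The case against.** The strongest reply is that this is a feasibility study. The Data Analysis section says power analyses and endpoints are not required for such studies. That excuses the missing power analysis and limits the weight of any p-value. It does not define a model, and the plan still names primary endpoints and two-sided tests for them.

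A second reply is that the method choice will seldom matter for pain. Entry needs a score of at least 5 and a 40% reduction in the stimulation trial, which is at least 0.40 × 5 = 2 points. If a 2-point fall is sustained (SDs 1.4 and 2.2, r = 0.4), the paired t test and centred ANCOVA disagree in 0.4% of samples, and at 2.80 points in under 0.01%. This stands for pain. Smaller effects remain possible for the other endpoints, for which no SDs are given.

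A third reply is that the dropout part is hypothetical: no dropout rate, mechanism, SD or correlation is stated. That is right. If loss is unrelated to outcome, the gain from the model is only a 2-10% smaller standard error, with 10-30% missing.

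A reader might also infer more than the documents support:
- That 6-month readings go unused when month 12 is missing. They still enter the 6-month comparison and are lost only to the 12-month estimate. NCS has no 6-month visit to lose.
- That every ANCOVA here is invalid. Sound forms exist, and adjustment for a baseline factor may be what was meant.
- That the analyst might treat the visits as independent groups. That is an unpaired test with no covariate, so it is not an ANCOVA, and it is an unlikely choice beside planned paired tests.
- That the 11-month pain score would repair the loss by a known amount. A score of 3 or more at that contact leads to a stimulator assessment before month 12, so month 12 may follow an intervention that a lost patient did not receive. No size can be put on this gain.

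The schedule figure is not shown and may add detail on time points.

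**Conclusion.** The concern holds and is worth fixing before analysis. The text plans two methods for the same comparisons, defines only one of them, and ranks neither. One natural version of the undefined method has a type I error of about 7-11% with equal SDs and r from 0.7 down to 0.3, or about 5.7% with SDs 1.4 and 2.2 and r = 0.4. It disagrees with the paired t test in about 4-7% of samples when the true fall is 1 point.

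The paired t test is valid with complete data. Its weakness at month 12 is modest: about 0.1-0.3 points of overstated benefit with 2-4 of 20 lost by 6-month pain. Against a sampling SD of about 0.5 and an assumed change of 2.80, that would not by itself overturn a pain result. All these sizes rest on assumed alpha, SDs, correlations and losses. The gap in the text does not depend on them.

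**What to change.** For endpoints measured at baseline, 6 and 12 months, including PHQ9, make the lead analysis one mixed model for repeated measures. Take all visits as outcomes, with visit as fixed effect, unstructured within-patient covariance and a small-sample degrees-of-freedom correction (Kenward-Roger is one option). Report mean change with 95% CI at 6 and 12 months and name the lead time point. First confirm from the schedule figure that NSC has a baseline reading, since Outcome Assessments lists it at 6 and 12 months only.

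Use the paired t test for two-visit endpoints (NCS, BMI, HgA1C). Do not use ANCOVA as a test of mean change. If covariate adjustment was intended, name the covariate and label that model exploratory.

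A sensitivity model with the 11-month pain score is optional. It must note the assessment triggered by a score of 3 or more at that contact. It also raises the covariance parameters from 6 to 10 with 20 patients.

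The cost is three or four sentences and a little more analysis work, with no new data. With complete data the mean change and standard error are those of the paired t test. The limit to state in the plan is that the model removes dropout bias only if loss depends on observed readings, and corrects only part of it otherwise.
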